Appendix 03: Breast milk intakes (added on 07.05.2013)

Contents

1.	Hypothesis to be tested	3
2.	Definition of the outcomes	3
3.	Basis for the analysis: Intention to treat and per protocol	3
4.	Time points for the analyses	1
5.	Presentation of the study findings and hypothesis testing	1
e i	5.1 Comparison of breast milk intakes and non-breast milk oral water intakes, among the ntervention groups at 9-12 months	4
6.	General notes on statistical methods	5
6	5.1 Software	5
6	5.2 Preparing breast milk data for analysis	5
6	5.3 Multiple comparisons	5
6	5.4 Confidence intervals	5
6	5.5 Covariate adjustment	5
7.	References	5
8.	Legends to the figures	5
9.	Figures	5
Fig	ure 1: Participant flow	7
10.	Tables)
7	Fable 1 Comparison in baseline characteristics)
[{	Fable 2 Comparison of breast milk intakes between children in the control and intervention groups, intention-to-treat analysis)
] I	Table 3 Comparison of breast milk intake between children consuming different daily doses of LNS, per protocol analysis	f 1

Study objective

To estimate breast milk intake in a sub-sample of Malawian infants participating in the LNS intervention trial at 9-12 months of age using the dose-to-mother deuterium oxide dilution technique.

1. Hypothesis to be tested

1. Mean breast milk intake (g/d) of 9-12 rural Malawian infants supplemented with 10-40 g/d of LNS is not lower than that of infants not supplemented with LNS.

2. Definition of the outcomes

Breast milk intake will be measured from deuterium oxide enrichment data using the solver function in excel. The breast milk intake estimate for each infant is calculated based on the two compartment steady state model between the mother and the infant (Shipley and Clark, 1972 as reported in IAEA manual for breast milk intake assessment). The output obtained after running the solver function is the mean breast milk intake (g/day) over a 14 day period. Breast milk intake will also be expressed as grams per kilogram body weight.

Mean non-breast milk oral water intakes and total daily water intake will be estimated in the same way as mean breast milk intakes.

3. Basis for the analysis: Intention to treat and per protocol

Primarily, the analysis will be based on the principle of modified intention-to-treat. The modification concerns six participants who were accidentally allocated to another group than originally randomized, as explained in the main analysis plan. Another modification to the intention to treat principle is that individuals with missing and incomplete data (as defined by participants from whom not all planned 7 time point saliva samples and weight measurements were taken) will be removed from the analysis.

As supplementary evidence, we will perform a per protocol analysis. For this analysis, participants will not be grouped based on their intended intervention, but rather by their observed actual LNS intakes. The actual intakes were determined with a modified 24 h recall on two separate days (approximately one week apart) during the breast milk intake assessment. The assessment categorized participants into four groups based on their actual LNS intake on the study days: None, 1-10 g, 11-20 g, and >20 g. In the per protocol analysis, we will use these

groups for the comparisons. Since not all the infants in breast milk intake study have dietary data, the per protocol analysis will be limited to participants with both breast milk and dietary intake data.

4. Time points for the analyses

The analysis for the study will primarily cover a two week period from when the participating infants are 9 to 12 months old.

5. Presentation of the study findings and hypothesis testing

6.1 Comparison of breast milk intakes and non-breast milk oral water intakes, among the intervention groups at 9-12 months

Box-whisker plots of the mean breast milk intakes in the 4 groups will be shown side by side in Figure 2. The group means and standard deviations for the intakes of breast milk, non-breast milk water and total water (in grams / day) will be presented as indicated in Table 2. Table 3 will tabulate the difference in mean breast milk intakes and their 90% confidence intervals between the control group and each of the intervention groups. Ninety per cent instead of 95% CI will be used because the non-inferiority consideration is one-sided and the use of 90% CI is the convention in this situation (Senn, 1997).

Evaluation

The set non-inferiority margin for this analysis will be 10% of the daily energy needs of infants corresponding to breast milk intake among 9-12 mo old infants. If the upper bound of the 90% CI for the point estimate for the difference in means (control mean minus intervention group mean) is smaller than the set margin of 10%, non-inferiority is confirmed. For instance if the difference between the control and any of the intervention is 40g with confidence interval of 30g to 60g, then that particular LNS dose is non-inferior to the control since the upper bound, 60g, is equivalent to about 6 % which is less that the non-inferiority margin (10%). If the lower bound of the 90% CI is larger than 10%, inferiority is confirmed. For example if the CI of the difference between the control and any of the LNS dose is 120g to 130g, since 120g is equivalent to about 11.8% which is above the noninferiority margin, the LNS dose in question would be considered inferior. If the upper and lower bounds of the 90% CI are larger and smaller, respectively, than 10%, the finding will be considered inconclusive for target group inference.

The set non-inferiority margin used in the present study (10% of the breast milk intake among control children) is based on clinical judgment and represents less than 10% of total daily energy needs of infants at 9-11 mo of age (Dewey and Brown 2003).

6. General notes on statistical methods

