6.4 Confidence intervals

The confidence intervals (CI) at 95% level will be provided for all the three main outcomes. The general group level comparison will also contain 95% CI which will be used to compare against the reported global mean intakes of breast milk, non-breast milk oral water intake and total water intake. Breast milk intake in the study will be considered significantly different if the lower CI of the group intakes is higher than the upper CI for the global reported intake. Confidence intervals will be based on t-test.

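### Appendix 3 sets the breast-milk non-inferiority margin on two unequal bases, and its tables do not show the 90% interval that the decision rule needs

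*SAP*

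**What the plan says.** All of this is in Appendix 3 of the SAP unless noted. Its single hypothesis is that mean breast milk intake at 9-12 months is not lower in supplemented infants than in controls.

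**Margin.** The Evaluation text in section 5 begins: "The set non-inferiority margin for this analysis will be 10% of the daily energy needs of infants corresponding to breast milk intake". Its last paragraph begins: "The set non-inferiority margin used in the present study (10% of the breast milk intake among control children", and says that this margin "represents less than 10% of total daily energy needs of infants at 9-11 mo of age".

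**Rule.** With the difference taken as control minus intervention, an upper 90% bound below the margin confirms non-inferiority. A lower 90% bound above it confirms inferiority. Anything else is inconclusive. Each branch gives the margin as 10% without saying of what.

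**Worked examples.** A 90% interval of 30 to 60 g is called non-inferior "since the upper bound, 60g, is equivalent to about 6" per cent. An interval of 120 to 130 g is called inferior because 120 g is put at about 11.8%. Neither example names its denominator.

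**Interval and table.** Section 5 states: "Table 3 will tabulate the difference in mean breast milk intakes and their 90% confidence intervals between the control group and each" intervention group, and justifies 90% by the one-sided question. Section 6.4 states: "The confidence intervals (CI) at 95% level will be provided for all the three main outcomes". The shells of Tables 2 and 3 both label the difference with a 95% CI. Table 2 is titled as the intention-to-treat analysis. Table 3 is the per-protocol analysis by actual LNS intake. Section 3 makes modified intention-to-treat primary and per protocol supplementary.

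**The concern.** A non-inferiority conclusion depends on its threshold. Here the threshold is described twice, and the second description says it is smaller than the first read literally. An analyst working only from this text cannot compute the margin in g/day, and the base could in effect be chosen after the intakes are known. Since this is the only hypothesis in the appendix, its whole conclusion rests on that choice.

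The reporting adds a smaller difficulty. The planned tables carry 95% intervals, so a reader who applies the rule to them uses a wider interval than the rule specifies. The text also points that reader to the table that does not hold the primary comparison.

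**Working it through.** **1. Reproduce the worked examples.**
- Inputs (section 5, Evaluation): 120 g is about 11.8%; 60 g is about 6%.
- Base = grams / proportion: 120 / 0.118 = 1,017 g/day. Rounding of 11.8% (11.75% to 11.85%) gives 1,021 to 1,013 g/day.
- Check on the other example: 60 / 1,017 = 5.9%, which agrees with about 6%.
- The two examples therefore share one base, and the implied margin is 0.10 x 1,017 = 101.7 g/day.

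**2. Compare the two definitions.** Let E be daily energy needs expressed as grams of breast milk and C the control-group mean intake.
- Opening sentence, read literally: margin = 0.10 x E.
- Closing paragraph: margin = 0.10 x C, stated to be less than a tenth of total energy needs, so 0.10 x C < 0.10 x E.
- The two are equal only if C = E, which the closing sentence excludes.

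**3. Size of the disagreement, if 1,017 g/day is E.** The SAP gives no value for C, so the range below is an assumption.

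| Assumed control intake, g/day | Control-based margin, g/day | Gap to 101.7, g/day |
|---|---|---|
| 700 | 70 | 31.7 |
| 800 | 80 | 21.7 |
| 900 | 90 | 11.7 |
| 1,000 | 100 | 1.7 |
| 1,017 | 101.7 | 0 |

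An upper 90% bound inside the gap gets two verdicts. Illustration with C = 800: a 90% CI of 30 to 90 g is non-inferior against 101.7 g (90 < 101.7) but inconclusive against 80 g (30 < 80 < 90). The document's own first example, 30 to 60 g, is non-inferior under both margins for C from 700 to 900.

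**4. If 1,017 g/day is C instead.** The examples then already follow the closing paragraph, and only the opening sentence is out of line. The text does not say which case applies.

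**5. Interval level.** Ratio of widths: 1.960 / 1.645 = 1.19. Illustration: a difference of 60 g with 90% half-width 38 g has a 90% CI of 22 to 98 g, non-inferior at 101.7 g. The 95% half-width is 38 x 1.19 = 45.3 g, so the 95% CI is 14.7 to 105.3 g, which would look inconclusive if the rule were applied to it.

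**The case against.** The strongest reply is that the intent can be recovered. The closing paragraph says which margin was used, and the reference to energy needs there reads as its justification. The opening sentence might loosely mean the energy supplied by breast milk, which would bring it close to the control-based margin. That is plausible and favours the control-based version, but the opening sentence does not say it, and as written it sets a different threshold.

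A second reply is that the g/day consequences are conditional. That is correct. The roughly 1,017 g/day base could be a control intake, in which case no verdict changes in the examples. A reader might infer that 102 g/day is the energy-based margin, or that the examples are wrong; the document supports neither.

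Third, a reader might infer from section 6.4 and the table shells that non-inferiority is judged at 95% in some places. It is not. Every branch of the rule uses 90%, main SAP section 12.4 reserves 90% for non-inferiority, and section 6.4 uses its 95% interval for comparison with globally reported intakes. What remains is a reporting mismatch.

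Fourth, the analysis population is not open: section 3 fixes modified intention-to-treat as primary. Naming Table 3 looks like a slip in the table number.

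Finally, this is a secondary analysis in a sub-sample, and Appendix 5 also examines breastfeeding in the full sample. That limits the reach of the problem but does not supply the missing base.

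**Conclusion.** The point holds on the margin: two bases, unequal by the appendix's own statement, with a rule and examples that name neither. If the examples use energy needs and control intake is 700-900 g/day (assumed), the margins differ by about 12 to 32 g/day, and an upper 90% bound in that gap is non-inferior under one definition and not under the other. The gap shrinks to 1.7 g/day at 1,000 g/day and disappears at about 1,017 g/day.

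The usual consequence is non-inferior against inconclusive. A reader might infer that outright opposite conclusions are likely. That would need a whole 90% interval between the two margins, for example 85 to 95 g against margins of 80 and 101.7 g. This is possible, but nothing in the document shows that intervals will be that narrow.

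On the interval, the finding is limited to reporting: the shells of Tables 2 and 3 do not show the 90% interval on which the rule depends, and the text directs the control-versus-intervention differences to the per-protocol table.

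**What to change.** In section 5 of Appendix 3:
- State one margin: 10% of the control-group mean breast milk intake, as the closing paragraph says was used, with the rule for turning it into g/day.
- Delete the energy-needs sentence, or reword it as supporting rationale only.
- Name the base of the worked examples. Change their percentages only if that base is not control intake.
- Refer to Table 2 for the intention-to-treat differences, and make it the decision table.

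In the tables and section 6.4:
- Print the 90% CI for the breast milk difference in Table 2.
- Keep the 95% CI in section 6.4 for the comparison with reported global intakes, and say that the non-inferiority decision uses 90%.

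The cost is wording and table headings. The control-based margin may be the stricter one, so non-inferiority may be somewhat harder to show. A confidence interval on the ratio of means, which would allow for the estimated control mean, is optional and not needed to remove the contradiction.

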6.1 Software

Analyses will be done in Stata version 12 and SAS for Windows version 9.3 (Cary, NC).

6.2 Preparing breast milk data for analysis

The first procedure in obtaining the breast milk intakes and non-breast milk oral water intake is to transfer the data from the solver output for each participant onto an excel file. Thus for all the participants their data were transferred to a common excel sheet from which suspicious values would be identified. Calculating the means for breast milk, non-breast milk oral intake and total water intake requires complete deuterium enrichment data to be used in the two compartment steady state model solver function in excel, this implies there are no missing data for participants who completed the study protocol.

6.3 Multiple comparisons

The initial plan is to compare means for intakes of breast milk, non-breast milk oral water and total water intakes using the global null hypothesis of no difference between groups. A trend analysis will then be conducted to find out if those receiving the dietary supplements at 10-40 g/d differ from the control group, which did not receive the study dietary supplements.

6.4 Confidence intervals

The confidence intervals (CI) at 95% level will be provided for all the three main outcomes. The general group level comparison will also contain 95% CI which will be used to compare against the reported global mean intakes of breast milk, non-breast milk oral water intake and total water intake. Breast milk intake in the study will be considered significantly different if the lower CI of the group intakes is higher than the upper CI for the global reported intake. Confidence intervals will be based on t-test.

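### Appendix 03's rule for comparing breast milk intake with the reported global figure cannot declare a shortfall, and interval non-overlap is not a 5% test (secondary comparison only)

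*SAP*

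**What the plan says.** Section 6.4 of Appendix 03 provides 95% confidence intervals for the three main outcomes and then adds a comparison with outside data: "The general group level comparison will also contain 95% CI which will be used to compare against the reported global mean intakes of breast milk", and likewise for the two water intakes. One decision rule follows, for breast milk only. Intake "will be considered significantly different if the lower CI of the group intakes is higher than the upper CI for the global reported intake". The section closes with "Confidence intervals will be based on t-test". It gives no condition for the opposite case, no test of the difference from the global figure and no interval for that difference.

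The hypothesis of the appendix (section 1) is a separate matter. It states that mean breast milk intake of supplemented infants "is not lower than that of infants not supplemented with LNS". The Evaluation text under section 5 assesses it with the 90% interval for control mean minus intervention mean and a 10% margin. That rule covers all three outcomes, including the adverse one: "If the lower bound of the 90% CI is larger than 10%, inferiority is confirmed".

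**The concern.** There are two defects in the section 6.4 rule.

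- **Direction.** The label is a significant difference, but the only condition is that the group lies above the global figure. If a group's whole interval lay below the global interval, an analyst following the text could not call it different.
- **Criterion.** Requiring one interval to clear the other is not the same as testing the difference at 5%. The standard errors are added directly rather than in quadrature, so the hurdle is too high whenever both figures carry error.

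At stake is a sentence in the report that places the study's intakes against reported global values. A clear shortfall would have to be described as not significantly different, and some real excesses would be missed.

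**Working it through.** The SAP gives no sample size, power or error rate for this comparison, so there is no figure to reproduce. The check is of the rule's operating characteristics.

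**Inputs**
- Group interval: 95%, t-based (section 6.4). The normal value 1.960 is used below, and the t-based version is checked by simulation.
- Global interval: its level is not stated; 95% is assumed.
- Standard errors: s1 for the group and s2 for the global figure, with r = s2/s1. The SAP gives no SD, sample size or global interval, so r is an assumption and is varied.

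**Critical value.** The lower group limit exceeds the upper global limit when

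difference > 1.960 × (s1 + s2).

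The standard error of the difference is sqrt(s1² + s2²), so the effective critical value is

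k = 1.960 × (1 + r) / sqrt(1 + r²).

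For example, at r = 1, k = 1.960 × 2 / 1.414 = 2.77. At r = 0.5, k = 1.960 × 1.5 / 1.118 = 2.63.

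**Size and power.** The size of the rule as written (upward only) is 1 − Φ(k). For power, take a true upward difference that a two-sided 5% test detects with 80% power, that is, 1.960 + 0.842 = 2.802 standard errors of the difference. The rule's power is then 1 − Φ(k − 2.802).

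| r | k | Size as written | Size if a mirror condition were added | Power, higher intake |
|---|---|---|---|---|
| 0 | 1.960 | 2.50% | 5.0% | 80% |
| 0.1 (or 10) | 2.145 | 1.60% | 3.2% | 74% |
| 0.2 | 2.306 | 1.05% | 2.1% | 69% |
| 0.5 (or 2) | 2.630 | 0.43% | 0.86% | 57% |
| 1 | 2.772 | 0.28% | 0.56% | 51% |

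Values for r and 1/r coincide because k is unchanged when the two standard errors swap places. The maximum of k is at r = 1, so equal standard errors are the worst case.

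**Lower intake.** If true intake is lower by the same 2.802 standard errors, the chance that the rule fires is 1 − Φ(k + 2.802). This is about 1 in a million at r = 0 and less at larger r. Such a result would also declare intake higher, which is the wrong direction. The chance of correctly declaring a shortfall is zero because no condition exists for it.

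**Check with t-based intervals.** Simulation with 200,000 runs per case and equal SDs gave upward size of 0.28% (50 v 50), 0.29% (100 v 100), 0.72% (50 v 500) and 1.58% (50 v 5000). These sample sizes are illustrative, not from the SAP. The results agree with the formula.

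**The case against.** The strongest objection concerns reach. A reader might infer from section 6.4 that the appendix cannot detect displacement of breast milk by LNS. The document does not support that. The hypothesis in section 1 compares supplemented infants with the trial's own unsupplemented infants, not with a global figure. The Evaluation rule can confirm inferiority against control, section 6.3 adds a global test and a trend analysis, and Tables 2 and 3 show differences from the control or zero-intake group with confidence intervals. This objection stands in full and confines the point to the external comparison.

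Second, little rests on that comparison. It appears only in the notes on confidence intervals, and no table shell or figure legend displays it. Group means and SDs are tabulated, so a low group would be visible. This also stands, and it keeps the severity low.

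Third, the size of the problem depends on a ratio that the SAP does not give. A reader might take the equal-standard-error figures (k = 2.77, 51% power) as the general result, but they are the worst case. If the global figure has negligible error, the upward part is exactly the upper half of an ordinary two-sided 5% test, and non-overlap costs nothing. That is why a range is shown.

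One could also argue that the mirror case is implied. The Evaluation text spells out every outcome of its own rule, so silence in section 6.4 is weak ground for reading one in. Even with it, the size reaches 5% only if the global figure has no error, and the rule itself refers to a confidence limit for that figure.

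**Conclusion.** The rule is wrong as written. It cannot declare breast milk intake lower than the reported global figure at any sample size. In the upward direction its size never exceeds 2.5%. Over the assumed range of r from 0 to 1 (and, by symmetry, above 1) it runs from 2.5% down to 0.28%, with power of 80% down to 51% where a two-sided 5% test has 80%. These figures assume that both intervals are 95% and that the two estimates are independent and approximately normal.

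Severity is low. The defect concerns a secondary, contextual comparison with external data. The test of LNS against control is not affected.

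**What to change.** Replace the decision sentence in section 6.4. Report the difference, group mean minus reported global mean, with a two-sided 95% confidence interval based on sqrt(SE_group² + SE_global²), and call intake different if that interval excludes zero in either direction. SE_global follows from the reported interval; for a 95% interval it is the width divided by 2 × 1.96. State the source and level of the global interval in the same place.

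The cost is SAP wording only. No new data are needed, because the existing rule already presupposes a confidence interval for the global figure.

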6.5 Covariate adjustment

Breast milk intakes, non-breast milk oral water intake, total water intake will be adjusted for infant baseline anthropometric indices.

7. References

Dewey, K. G. & Brown, K. H. Update on technical issues concerning complementary feeding of young children in developing countries and implications for intervention programs. *Food and nutrition bulletin* **24**, 5-28 (2003).

Senn S. Statistical Issues in Drug Development. Chichester, GBR. John Wiley & Sons. 1997.

8. Legends to the figures

Figure 1. Participant flow

Figure 2. Box-Whisker plots of breast milk intakes by groups

9. Figures

Figure 1: Participant flow

Figure 2. Box-Whisker plots of breast milk intakes by the intervention group

10. Tables

Table 1 Comparison in baseline characteristics

Variable	Control	10g milk LNS	20g LNS	40g LNS	Test
Number of participants	XXX	XXX	XXX	XXX	
Infants characteristics					
Age, months (mean, SD, N)	xx.x (xx.x)	xx.x (xx.x)	xx.x (xx.x)	xx.x (xx.x)	ANOVA
Proportion of Males (percentage)	xxx / xxx (xx%)	xxx/ xxx (xx%)	xxx/ xxx (xx%)	xxx/ xxx (xx%)	Chi-squared
Weight, kg (mean, SD, N)	xx.x (xx.x)	xx.x (xx.x)	xx.x (xx.x)	xx.x (xx.x)	ANOVA
Maternal characteristics					
Age, year (mean, SD, N)	xx.x (xx.x)	xx.x (xx.x)	xx.x (xx.x)	xx.x (xx.x)	ANOVA
Height, kg (mean, SD, N)	xxx.x (xx.x)	xxx.x (xx.x)	xxx.x (xx.x)	xxx.x (xx.x)	ANOVA
Weight, kg (mean, SD, N)	xx.x (xx.x)	xx.x (xx.x)	xx.x (xx.x)	xx.x (xx.x)	ANOVA
BMI, kg/m ² (mean, SD, N)	xx.x (xx.x)	xx.x (xx.x)	xx.x (xx.x)	xx.x (xx.x)	ANOVA

	Planned daily dose of LNS, grams / day						
Variable	Control, 0g LNS	10g LNS	20g LNS	40g LNS			
Mean (SD) breast milk intake, grams / day	xxx.x (xx.x)	xxx.x (xx.x)	xxx.x (xx.x)	xxx.x (xx.x)			
Difference (95% CI) in mean intakes between the indicated intervention group and the control		X.XX	X.XX	X.XX			
Mean non-breast milk oral water intake (SD)	xxx.x (xx.x)	xxx.x (xx.x)	xxx.x (xx.x)	xxx.x (xx.x)			
Difference (95% CI) in mean intakes between the intervention and control groups		X.XX	X.XX	X.XX			
Mean total water intake (SD)	xxx.x (xx.x)	xxx.x (xx.x)	xxx.x (xx.x)	xxx.x (xx.x)			
Difference (95% CI) in mean intakes between the intervention and control groups		X.XX	X.XX	X.XX			

Table 2 Comparison of breast milk intakes between children in the control and intervention groups, intention-to-treat analysis

	Actual daily intake of LNS, grams / day						
Variable	0	1 – 10	11 - 20	> 20			
Mean (SD) breast milk intake, grams / day	xxx.x (xx.x)	xxx.x (xx.x)	xxx.x (xx.x)	xxx.x (xx.x)			
Difference (95% CI) in mean intakes between the indicated intervention group and the control		X.XX	X.XX	X.XX			
Mean non-breast milk oral water intake (SD)	xxx.x (xx.x)	xxx.x (xx.x)	XXX.X (XX.X)	xxx.x (xx.x)			
Difference (95% CI) in mean intakes between the intervention and control groups		X.XX	X.XX	X.XX			
Mean total water intake (SD)	xxx.x (xx.x)	xxx.x (xx.x)	XXX.X (XX.X)	xxx.x (xx.x)			
Difference (95% CI) in mean intakes between the intervention and control groups		X.XX	X.XX	X.XX			

Table 3 Comparison of breast milk intake between children consuming different daily doses of LNS, per protocol analysis

Prevention of Linear Growth Faltering in Infants and Young Children With Lipidbased Nutrient Supplements (iLiNS-DOSE)

Statistical Analysis Plan

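### Appendix 3 orders baseline adjustment of breast milk intake but does not say whether the adjusted or the t-test interval decides non-inferiority

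*SAP*

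**What the plan says.** The only hypothesis in Appendix 3 is that mean breast milk intake in supplemented infants is not lower than in controls. Four places bear on how the deciding interval is built.

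- **Covariate adjustment (6.5).** "Breast milk intakes, non-breast milk oral water intake, total water intake will be adjusted for infant baseline anthropometric indices". This sentence is the whole section. It names no model and no indices, and gives the adjusted result neither primary nor secondary status.
- **Confidence intervals (6.4).** "The confidence intervals (CI) at 95% level will be provided for all the three main outcomes", and at the end of the same paragraph, "Confidence intervals will be based on t-test".
- **Presentation and Evaluation (section 5).** "Ninety per cent instead of 95% CI will be used because the non-inferiority consideration is one-sided". The verdict is read from the "upper bound of the 90% CI for the point estimate for the difference in means (control mean minus intervention group mean"), and no covariates are mentioned.
- **Table shells.** Table 2 gives group mean (SD) and a row headed "Difference (95% CI) in mean intakes between the indicated intervention group and the control". Table 3 has the same rows for the per-protocol groups. Neither has a row or column for an adjusted result.

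**The concern.** Non-inferiority turns on whether one confidence bound crosses one margin. An adjusted and an unadjusted interval for the same contrast will usually differ in both centre and width. Where the bound lies near the margin, one can confirm non-inferiority while the other is inconclusive. Because the plan orders an adjustment without saying what it is for, the choice could be made after both results are seen. The analysis is confined to a sub-sample, so interval width may well matter to the verdict.

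Other parts of the SAP settle this point. Main section 12.6 lists four models and a 10% change rule. Appendix 4 (7.7) and Appendix 8 (10.5) make the unadjusted analysis the main one and the adjusted analysis secondary. Appendix 5 (5.4 and 5.5) takes its equivalence intervals from ANCOVA with listed covariates. Section 6.5 of Appendix 3 neither gives a rule of its own nor refers to the main plan's.

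**Working it through.** **Step 1: look for a link between the adjustment and the verdict.** Section 6.5 covers all three intakes but is silent on intervals. Section 6.4 covers intervals, at the 95% level, but is silent on covariates. Section 5 uses a 90% interval, names no estimation method and mentions no covariates. It sends the 90% intervals to Table 3, but the Table 3 shell is the per-protocol table, and both shells are labelled 95%. Nothing connects 6.5 to the deciding interval, and that 90% interval has no shell at all.

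**Step 2: the margin in grams.** Appendix 3 states no sample size, SD, power or expected precision, so it has no precision figure to reproduce. Its worked example equates 120 g with about 11.8%. The implied reference intake is 120 / 0.118 = 1,017 g/day, and 10% of that is about 101.7 g/day. The example's other figure agrees: 60 / 1,017 = 5.9%, which the SAP gives as about 6%.

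**Step 3: effect of adjustment on width.** The ratio of adjusted to unadjusted width is about √(1 − R²), where R² is the share of within-group variance in intake explained by the covariates. R² is an assumption; the SAP gives none.

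| R² | √(1 − R²) | Narrower by |
|---|---|---|
| 0% | 1.000 | 0% |
| 2% | 0.990 | 1.0% |
| 5% | 0.975 | 2.5% |
| 10% | 0.949 | 5.1% |
| 20% | 0.894 | 10.6% |

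With four groups and q covariates, the cost in degrees of freedom multiplies the ratio by about √((N − 5)/(N − 5 − q)). For q = 3 and R² = 0 this gives √(115/112) = 1.013 at N = 120 and √(315/312) = 1.005 at N = 320. If baseline size does not predict intake, adjustment therefore widens the interval by 0.5% to 1.3%.

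**Step 4: can the verdicts differ?** Take the 40 g difference from the SAP's example and suppose that both analyses give it. The room to the margin is 101.7 − 40 = 61.7 g. The t-test interval is inconclusive once its half-width exceeds 61.7 g. The adjusted interval still confirms non-inferiority while the t-test half-width is below 61.7 / √(1 − R²):

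- R² = 5%: 61.7 / 0.975 = 63.3 g
- R² = 10%: 61.7 / 0.949 = 65.0 g
- R² = 20%: 61.7 / 0.894 = 69.0 g

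The verdicts split when the t-test half-width lies between 61.7 g and these values. Adjustment also moves the point estimate when baseline size is unbalanced by chance, so a split can arise outside this band.

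**Step 5: illustrative power.** Power = Φ(margin / (SD·√(2/n)·√(1 − R²)) − 1.645), with a true difference of zero. Assuming SD 200 g and 50 infants per group, the unadjusted standard error is 200·√(2/50) = 40 g. Power is Φ(101.7/40 − 1.645) = 81.5% unadjusted, and 83.2%, 85.0% and 88.4% at R² of 5%, 10% and 20%. Over assumed values of 30 to 100 per group and SD 150 to 250 g, the gain at R² = 10% is never more than about 4 points.

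**The case against.** A reader might infer that the adjustment cannot enter the verdict at all, because a two-sample t-test takes no covariates. The SAP does not support that. Main section 12.4 uses the same t-test wording for quantitative outcomes and covers 90% intervals for non-inferiority, yet main section 11.4 takes its non-inferiority interval from a regression coefficient. In this SAP the phrase does not rule out a t-based interval from a linear model. The t-test sentence in 6.4 also closes a paragraph on 95% intervals, not on the 90% interval that decides.

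A reader might also infer that an unadjusted verdict would be wrong. It would not. The comparison by allocated group is protected by randomisation, and the exclusion of infants with incomplete samples affects both analyses alike. Leaving out age at measurement and sex is not an error either. They could add precision, since infants are measured between 9 and 12 months, but validity does not need them.

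It is fair to add that the precision argument is conditional and may be small, and that a missing row in a table shell is only a presentation gap. What remains is narrower: an adjustment is ordered, no role is given to it, and the deciding interval is not identified. The per-protocol analysis adds some weight. It regroups infants by observed intake, so randomisation does not protect it, and there the choice of covariates bears on bias as well as precision.

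**Conclusion.** The point holds as an under-specified and internally unreconciled instruction. Sections 6.4, 6.5 and the Evaluation rule do not together identify one interval, and the two candidates can give different verdicts when the bound lies near the margin. It does not hold as a claim that the plan's verdict is invalid, or that it must lose precision. The likely gain is about 2.5% of interval width at R² = 5%, 5% at 10% and 11% at 20%, before a small cost in degrees of freedom, and nothing if baseline size does not predict intake. These sizes rest on assumed R² values. The open choice between the two intervals rests on no assumption.

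**What to change.** - **Section 6.5:** specify one ANCOVA per outcome, with group (control, 10, 20, 40 g) and named baseline indices, for example weight or the z-scores. Define baseline as trial enrolment. Weight at the 9-12 month measurement comes after randomisation and should not be used. Infant age at measurement and sex may be added as optional precision covariates.
- **Section 5, Evaluation:** state that the 90% interval from this model decides non-inferiority for breast milk intake.
- **Section 6.4:** replace the t-test sentence with a reference to the model.
- **Table 2:** add the adjusted difference with its 90% interval, keep the t-test difference as supportive, and correct the reference that sends the 90% intervals to Table 3.

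The same edit should fix the margin. The Evaluation text defines it once as a share of energy needs ("The set non-inferiority margin for this analysis will be 10% of the daily energy needs of infants") and later as a share of control infants' breast milk intake. If the second is meant, say whether the raw or the adjusted control mean is used.

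The cost is a few sentences and one regression per outcome. Weight and length at enrolment are already collected for the main analysis.
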